7.2 Baseline

Unless stated otherwise, baseline is defined as the last non-missing observation made prior to the first administration of IMP. if multiple values pre-treatment exists then the value closes to first treatment administration will be considered as baseline.

7.3 Stratifications

For analysis purposes, we are not doing any stratification and we will provide summary by treatment (i.e. Basaglar).

7.4 Statistical tests

This is the single arm study so no comparison tests will be performed.

The incidence of hypoglycemia will be analysed using the exact binomial method (Clopper-Pearson method) for single proportions. The change from baseline (e.g. for HbA1c, FBG levels etc) will be analysed using the general linear model and the baseline visits of the respective parameter will be considered as covariate. The rates

of hypoglycemia will be analysed using the Negative Binomial Model without categorical variable i.e. the generalized linear model and the baseline visit of HbA1c will be considered as covariate.

7.5 Common calculations

For quantitative measurements, change from baseline will be calculated as: (Test value at Visit Day X – Baseline value), where the baseline value is defined as the last non-missing observation taken prior to first exposure to IMP.

7.6 Software

All analyses will be conducted using SAS® Version 9.4 and above.

8. Statistical considerations

8.1 Multicentre studies

Approximately 295 subjects will be screened, so that 250 subjects can be enrolled. the target is to have a minimum of 200 subjects completing the present study and the study visits will be conducted at different sites in India.

8.2 Missing data

- Vital Signs: we will use the last observation carry forward (LOCF) method for the missing values.
- 2) Actual and Change from Baseline HbA1c: For subjects requiring rescue medication, HbA1c values recorded after the first administration of rescue medication will not be considered for analysis, and these values will be considered as missing. In addition, for the actual value and change from baseline, a descriptive analysis using LOCF will be performed, using the baseline or 12-week value, if the 24-week value is missing or occurred after use of rescue medication.
- 3) Subjects Reaching HbA1c Targets (≤6.5% and <7%) at Week 24: The HbA1c values used to calculate this binary variable will be the LOCF value, that is, in case the Week 24 value is missing, the Week 12 value will be used. The denominator will be the total FAS population. Subject with missing HbA1c data at Week 12 and Week 24 will be considered as not having reached the target.

For other efficacy parameters 7-point SMBG levels (mg/dL and mmol/L), body mass index (kg/m²), body weight (kg), basal insulin dose (U/day and U/kg/day) we will apply the LOCF method for missing data.

4) ITSQ score: If an item score is missing for a subject and ≤20% of the items within the domain (or overall) are missing for that subject, then the mean of the items scores in the domain (or overall) will be imputed for the missing item score(s). If there are >20% missing items, the individual subject domain (or overall) score will be set to missing. that is here we will use the mean imputation method.

Page 25 of 85

Change at Week 24 from Week 4 for ITSQ score (Transformed overall and domain scores): we will use the last observation carry forward (LOCF) method for the missing values.

5) Laboratory data: we will use the last observation carry forward (LOCF) method for the missing values.

For all other cases the missing data will not be imputed for this trial.

9. Output presentations

This is single arm study; we are not doing any stratification we will present the summary table for single treatment group i.e. Basaglar.

The Section 23, Appendix 1 describe the format and content for presentation of tables, listings and figures (TLFs).

All percentages (%) for a specific summary are calculated using the total number of participants included in the relevant analysis population as the denominator, unless otherwise specified.

Data listings will be based on all participants, unless otherwise specified.

In general, if we have no response or record for respective parameter in data (i.e. n=0) then while presenting statistics in table only n will be presented as "0" and other statistics will be left blank. In case, we have only one response or record for respective parameter (i.e. n=1) in data then statistic (S.D) in table will be presented blank.

By default, for continuous measures, summary statistics will include, unless otherwise specified:

- Sample Size (N)
- n
- Mean
- Median
- Maximum
- Minimum
- Interquartile Range
- SDs, and
- Frequency of Missing Values.

For categorical measures, summary statistics will include, unless otherwise specified:

- Sample Size (N)
- Frequency of non-missing values
- Percentage, and

Page 27 of 85

• Frequency of Missing Values.

For efficacy tables, below statistics will be included, unless otherwise specified:

- Estimate
- 95 % Confidence Interval
- P-value

I4L-IN-ABEX(b)

10. Participant disposition and withdrawal

10.1 Variables and derivations

The trial classifications are defined as follows:

Screening failure:

Individuals who do not meet the criteria for participation in this study (screen failure) at the initial visit may be later rescreened only once. The interval between screening and rescreening should be at least 4 weeks.

Completed treatment:

All the subject who have taken all the treatment as per protocol.

Completed trial:

Participants who completed the trial, as indicated on the [End of Study] page of the (eCRF), will be assumed to have completed trial.

Lost to follow-up:

A subject will be considered lost to follow-up if he or she repeatedly fails to return for scheduled visits and is unable to be contacted by the study site. Site personnel are expected to make diligent attempts to contact subjects who fail to return for a scheduled visit or were otherwise unable to be followed up by the site.

Early withdrew from trial:

Participants who discontinued from the trial, as indicated on the [End of Study] page of the (eCRF), will be assumed to have withdrew early from trial.

The following parameters will be summarised for the subject's disposition table as per eCRF:

- Number of screening failure subjects (This will be applicable for ENRL set table only.)
- Number of subject's completed trial
- Number of subject's completed treatment
- Number of subjects withdrew early from trial

- Number of Subject's in ENRL set
- Number of Subject's in FAS set
- Number of Subject's in PP set

The following parameters will be summarised for the early withdrawals table as per eCRF Subject's primary reason for discontinuation (reasons mentioned in eCRF "End of the Study" form) which is as follows:

- ADVERSE EVENT
- DEATH
- SCREEN FAILURE
- WITHDRAWAL BY SUBJECT
- PHYSICIAN DECISION
- NON-COMPLIANCE WITH STUDY DRUG
- PROTOCOL DEVIATION
- STUDY TERMINATED BY IRB OR ERB
- STUDY TERMINATED BY SPONSOR
- LOST TO FOLLOW-UP
- LACK OF EFFICACY
- OTHER

Derivations:

- In eCRF at End of the study form primary reason for discontinuation is indicated as "SCREEN FAILURE" to ensure that subject is screen failure.
- In eCRF at End of Study form Subject status is indicated as "COMPLETED" to ensure that subject is completed trail.
- If the date of last dose of study treatment < Date of Visit (Visit 8(Week 24)) and date of last dose of study treatment > Date of Visit (visit 7(week 20)) to ensure that subjects is completed treatment.
- In eCRF at End of Study form Subject status is indicated as "DISCONTINUED" to ensure that subjects withdrew early from trial.
- In eCRF at End of Study form the subject's primary reason for discontinuation is indicated as "LOST TO FOLLOW-UP" to ensure that subjects lost to followup form trial.

The following variables will be listed for the subject's disposition:

- Subject Number
- Informed consent date
- Last dose administration date
- Subject study status
- Date of completion/discontinuation
- Subject's primary reason for discontinuation
- Death date

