Procedure	Screening	Treatment Period							Follow-up	Notes
Visit	1	2	3	4	5	6 a	7 a	8	9/ET	
Week of Study	-2	0	4	8	12	16	20	24	28	
Allowable Deviation +/- (days)		3	7	7	7	7	7	7		
Self-titration training c		X	X	X	X	X	X	X		This training is given at baseline and reinforced at every visit of the treatment period
Dispense study diary	X	X								Pretreatment study diary will be dispensed at Visit 1 and comprehensive study diary will be dispensed at Visit 2
Dispense study drug		X	X	X	X					
Review study diary		X	X	X	X			X		Pretreatment study diary will be collected at Visit 2 and comprehensive study diary will be collected at Visit 8
Collect unused study drug			X	X	X			X		
Dispense glucometer	X									
Compliance to study drug administration		X	X	X	X	X	X	X		
Adjust insulin dose (if required)			X	X	X			X		Site personnel will review the Basaglar dose and FBG levels recorded in the subject diary. They may recommend change in dose of Basaglar if required.

Abbreviations: AE = adverse event; CV = cardiovascular; DBP = diastolic blood pressure; ECG = electrocardiogram; ET = early termination; FBG = fasting blood glucose; HbA1c = glycated hemoglobin; HIV = human immunodeficiency virus; ITSQ = Insulin Treatment Satisfaction Questionnaire; PR = pulse rate; SAE = serious adverse event; SBP = systolic blood pressure; SMBG = self-monitored blood glucose; WCBP = women of child-bearing potential.

- a Telephone visit.
- b All vital signs should be recorded in the subject in a resting state. If there is a suspicion of postural hypotension or autonomic instability, the investigators at their discretion might decide to record the blood pressure in a supine state and then after standing for 2 minutes to detect any postural hypotension. Blood pressure measurements should be done in the left arm with sphygmomanometer held at the level of the heart. Blood pressure recording in both arms is at the investigators' discretion in selective cases of pulse volume inequality or pulse being absent in either of the arms.
- c Subjects will be instructed to daily measure the FBG levels mandatorily using glucometer before the morning meal till Week 12 and record in the subject diary. Also, subjects will be instructed to measure and record the blood glucose levels using glucometer if they have symptoms of hypoglycemia (including nocturnal hypoglycemia) at any time of the day or night.

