## 5. Study Design

### 5.1. Overall Design

Study I4L-IN-ABEX (ABEX) is a multicenter, open-label, single-arm, Phase 4 study to assess the safety of Basaglar in subjects with T2DM in India.

The study design includes the following periods:

[figure not shown]
- Screening (Week -2 to Week 0)
- Treatment
  - Titration period (Week 0 to Week 12)
  - Maintenance period (Week 12 to 24)
- Safety Follow-up (Week 28)

Week 0 to Week 12 will be the titration phase followed by the maintenance phase till Week 24. Approximately 295 subjects will be screened as per the inclusion and exclusion criteria mentioned in Sections [6.1](#) and [6.2](#), respectively, so that 250 subjects can be enrolled in the study, with a target to have a minimum of 200 subjects completing the present study. Subjects will be screened at Visit 1 and eligible subjects will be administered with Basaglar once daily (QD) from Visit 2 for a period of 24 weeks.

The starting dose will be 10 units QD. All subjects will be trained at Screening (Visit 1) on insulin injection administration technique, use of glucometer, and 7-point SMBG measurement. These trainings will be reinforced at every face-to-face visit of the treatment period. Subjects will self-administer Basaglar at bedtime. The doses may be titrated by 2-4 units once or twice in a week until FBG levels are lowered to <100 mg/dL (5.6 mmol/L).

Study governance considerations are described in detail in [Appendix 3](#).

Figure [ABEX.1](#) illustrates the study design.

\*Telephone visit

Abbreviations: GLP-1 RA = glucagon-like peptide-1 receptor agonist; OAM = oral antihyperglycemic medications; QD = once daily.

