### **7.2.1. Selection and Timing of Doses**

Subjects will self-administer the insulin every day at bedtime after dinner. Patients will record the actual time and dose of all administrations of Basaglar in the subject diary. Later, these data will be recorded in the subjects' electronic case report form (eCRF).

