7.1 Visit and date conventions

Visit day will be calculated from the reference start date which will be used to present start/stop day of assessments and events. The *reference start date* is defined as the date of first IMP administration. The following conventions will be used for event references:

Date of event less than reference treatment start date

• Event day = date of event - reference treatment start date

[figure not shown]
Date of event greater than equal to reference treatment start date

• Event day = date of event - reference treatment start date + 1

Above two formulae will be use for the calculation of the duration (in days) for the respective events (i.e. AEs etc).

Visit windowing (i.e. remapping of visits based on visit windows) will be performed for this trial. The assigned nominal visit will be used for by-visit summaries. In the situation where the assessment/event date is partial or missing, visit day/week, and any corresponding durations will appear missing in the data listings. Unscheduled measurements will not be included in by-visit summaries. Data listings will include scheduled, unscheduled, and early discontinuation data. The following figure 7.1 illustrates the study design.

Figure 7.1

*Telephone visit

Abbreviations: GLP-1 RA = glucagon-like peptide-1 receptor agonist; OAM = oral antihyperglycemic medications; QD = once daily.

The study design includes the following periods:

- Screening (Week -2 to Week 0)
- Treatment period
 - Titration period (Week 0 to Week 12)
 - Maintenance period (Week 12 to 24)
- Safety Follow-up (Week 28)

Trial visit will be assigned as delineated in Table 7.1:

| | Screen | | | Follow-up | | | | | | |
|-----------------------------------|----------|---|----|-----------|----|-----|-----|-----|-------|--|
| Visit Day | -14 to 0 | 0 | 28 | 56 | 84 | 112 | 140 | 168 | 196 | |
| Visit Week | -2 | 0 | 4 | 8 | 12 | 16 | 20 | 24 | 28 | |
| Visit No. | 1 | 2 | 3 | 4 | 5 | 6 | 7 | 8 | 9 /ET | |
| Allowable Deviation +/- (days) | | 3 | 7 | 7 | 7 | 7 | 7 | 7 | | |

The below detail mentioned procedures will be completed at each visit:

Screening period (Week -2 to Week 0) i.e. Visit 1

The following procedures will be completed for each study participant:

- Informed consent
- Inclusion / Exclusion Criteria
- Demographic information
- HIV and Hepatitis testing
- Physical Examination
- Vital Signs
- Medical History and family history of CV disease
- History of substance usage
- 12-lead ECG

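### The completed-treatment derivation in SAP 10.1 counts subjects who stop drug soon after Week 20 but still attend Visit 8, contrary to the SAP's own definition

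*SAP*

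**What the plan says.** SAP 10.1 gives both a definition and a derivation of completed treatment.

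- Definition: "All the subject who have taken all the treatment as per protocol".
- Derivation, upper bound: "If the date of last dose of study treatment < Date of Visit (Visit 8(Week 24".
- Derivation, lower bound: "date of last dose of study treatment > Date of Visit (visit 7(week 20".

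Both inequalities are strict. The derivation has no condition on duration, missed doses or completion status. The number of subjects who completed treatment is then a planned row of the disposition table, separate from the row for subjects who completed the trial.

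The planned course is set in Protocol 5.1: "eligible subjects will be administered with Basaglar once daily (QD) from Visit 2 for a period of 24 weeks". Protocol 7.2.1 sets the time of day: "Subjects will self-administer the insulin every day at bedtime after dinner". SAP Table 7.1 places Visit 2 at Day 0, Visit 7 at Day 140, Visit 8 at Day 168 and Visit 9 at Day 196, with 7 days' tolerance either side at Visits 3 to 8.

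**The concern.** The derivation does not implement the definition. The lower bound sits at the Week 20 telephone visit, four weeks before treatment is due to end. Anyone whose last dose falls in those four weeks, and who later attends Visit 8, is labelled a treatment completer. Protocol 8.1.1 asks subjects who stop drug early to complete safety follow-up under the Schedule of Activities, so attending Visit 8 off drug is foreseeable.

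At stake is one descriptive count. In a single-arm safety study, readers will use that row to judge how many subjects had the full 24 weeks of exposure, and SAP 12.2 plans exposure as a listing only. The row could also contradict other rules in the plan. Protocol 7.6 regards a subject who misses more than 3 consecutive days as withdrawn, and PPS criterion (c) excludes anyone off drug for more than 14 consecutive days.

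**Working it through.** **The plan's own figures.** The plan gives no expected number of treatment completers. Its headcounts reproduce and are not in dispute: 200 / (1 − 0.20) = 250 enrolled, and 250 / (1 − 0.15) = 294.1, rounded up to 295 screened.

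**Inputs.** Visit days and windows come from SAP Table 7.1 ("Visit Day | -14 to 0 | 0 | 28 | 56 | 84 | 112 | 140 | 168 | 196" and "Allowable Deviation +/- (days) | | 3 | 7 | 7 | 7 | 7 | 7 | 7"). Dosing is once daily at bedtime. I assume that the first dose is on the evening of Day 0. The plan is then 24 × 7 = 168 doses, on Days 0 to 167.

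**Rule tested.** Visit 7 date < last dose date < Visit 8 date. For a last dose on day L:

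- doses taken = L + 1
- doses missed before Visit 8 = (Visit 8 day − 1) − L

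**Nominal visits (Visit 7 on Day 140, Visit 8 on Day 168).**

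| Last dose | Meets the rule? | Consecutive doses missed before Visit 8 | More than 14 (PPS c)? | More than 3 (Protocol 7.6)? |
|---|---|---|---|---|
| Day 140 | No | 27 | Yes | Yes |
| Day 141 | Yes | 26 | Yes | Yes |
| Day 152 | Yes | 15 | Yes | Yes |
| Day 153 | Yes | 14 | No | Yes |
| Day 163 | Yes | 4 | No | Yes |
| Day 164 | Yes | 3 | No | No |
| Day 167 | Yes | 0 | No | No |
| Day 168 | No | 0 | No | No |

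A last dose on Day 141 means 142 doses taken and 168 − 142 = 26 missed; 26 / 168 = 15.5%. Last doses on Days 141 to 152 pass although more than 14 consecutive days are missed. Those on Days 141 to 163 pass although more than 3 are missed.

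**Largest gap that passes within the visit windows.**

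- Visit 7 on Day 133, Visit 8 on Day 175: the earliest passing last dose is Day 134, and 174 − 134 = 40 doses are missed before Visit 8.
- Visit 7 on Day 147, Visit 8 on Day 161: the earliest passing last dose is Day 148, and 160 − 148 = 12 doses are missed.

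**Upper bound.** A last dose dated on Visit 8 fails. The documents point both ways on whether this will happen:

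- Against: 168 bedtime doses from Day 0 end on Day 167, which passes. The Schedule of Activities marks "Collect unused study drug" at Visit 8 and no dispensing there, so the expected last dose is the evening before.
- For: Protocol 5.1.1 places the follow-up visit four weeks after the last dose. Visit 9 is Day 196, and 196 − 28 = 168, the Visit 8 day. The schedule also marks insulin dose adjustment at Visit 8.

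**The case against.** The strongest reply is that little depends on this flag. The FAS needs one dose. The PPS derivation uses the completion or discontinuation date against Visit 8, plus major deviations. The primary endpoint uses event dates, and the rate offsets use first and last dose dates. Last-dose dates are also listed by subject, so the row can be recomputed. All of this stands, and it confines the point to one disposition row.

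Three stronger readings are tempting, and the documents do not support them.

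- **Any last dose after Week 20 counts.** It does not. The rule also needs a Visit 8 date later than the last dose, so a subject who stops at Week 21 and leaves the study without a Visit 8 is not counted.
- **Completers are misclassified equally in both directions.** A completer on the nominal schedule, with a last dose on Day 167, is classified correctly. Failure through a dose dated on Visit 8 is possible but not shown to be routine.
- **The regulatory figure of 200 is at risk.** Protocol 3.1 reports a request to study at least 200 additional local subjects and states no treatment duration. The plan's target is 200 subjects completing the study, which SAP 10.1 counts from the End of Study status.

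It can also be said that subjects with long gaps should appear as withdrawn under Protocol 7.6. They should, but the completed-treatment derivation does not look at that status, so the same subject could appear in both rows.

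**Conclusion.** The point holds in limited form. The derivation contradicts its own definition and can count as a completer someone who missed 26 of 168 doses (15.5%) at nominal visits, or up to 40 doses before Visit 8 at the extremes of the windows. The strict upper bound is a secondary weakness of unknown frequency. The effect stays within the completed-treatment row of the disposition table.

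These figures assume a first dose on Day 0, one bedtime dose a day until the last dose, and attendance at Visit 8. The number of subjects affected cannot be estimated, because the documents give no distribution of last-dose dates. It is worth correcting before database lock because the stated rule can give a wrong count and is cheap to repair.

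**What to change.** In SAP 10.1:

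1. Delete the condition that the last dose precedes Visit 8.
2. Replace the Visit 7 lower bound with one tied to the end of planned treatment. For example, require that Visit 8 was attended and that the last dose is no more than 3 full days short of the earlier of Visit 8 or 24 weeks, using the missed-dose threshold in Protocol 7.6. As a formula: last dose date ≥ min(Visit 8 date, first dose date + 168 days) − 4 days. At nominal visits, Day 164 passes (3 doses missed), Day 163 fails (4 missed) and Day 168 passes. A subject who finishes on Day 167 and has Visit 8 on Day 175 also passes. A one-day cut-off before Visit 8 would fail that subject, and would also fail someone who missed only the final evening's dose.
3. Classify subjects with a missing Visit 8 date or last-dose date as not completed.

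This rule addresses early stopping only. Gaps earlier in treatment remain with the compliance summary in SAP 13, and the definition should say so.

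The cost is a sentence or two of SAP text and one line of code, with no change to study conduct. The reported number of treatment completers may change slightly.

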10.2 Analysis

Population: ENRL and FAS

Stratification: Table: NA

Listing: By subject

Statistics: Participants disposition and Withdrawal will be summarised frequency and percentages and the screening failure subjects will be summarised (frequency) by total for table. The listing will be provided.

11. Participant demographics and other baseline characteristics

11.1 Variables and derivations

The following demographic and other baseline characteristics will be summarized:

- Age (in Years) (Calculated relative to date of informed consent in eCRF)
- Gender
- Race
- Height (cms) at Screening
- Weight (kgs) at Screening
- BMI (kg/m²) at Screening

Note: For Age Calculation according to Lily standards for the Date of birth only year field will population in the dataset, and day and month will come as unknown so, we will consider it as 01JUL for back end calculation.

Age (Years) and BMI (kg/m²) will be calculated as follows:

- Age (Years) = $floor \left[\frac{Date of informed consent Date of birth}{365.25}\right]$
- $BMI(kg/m^2) = \frac{weight(kgs)}{\left[\frac{height(cms)}{100}\right]^2}$

The following demographic and baseline characteristics will be listed:

- Subject number
- Informed consent date
- Year of birth
- Age (in years)
- Gender
- Race
- BMI

Below parameters will be provided in septate listing:

12 Lead ECG

CONFIDENTIAL CS.BS.01.00 TPL-1.0: Statistical Analysis Plan Template

Page 32 of 85

- Serum Pregnancy Test
- HIV and Hepatitis testing

